8.4.8 Dose Escalation Rule

The window used for assessing DLTs in this study is 10 weeks. In the TITE-BOIN dose escalation design, the risk of a DLT is assumed to increase over the 10-week DLT assessment period. We operationalize this assumption by breaking up the DLT assessment period into thirds (3.33 weeks) and distribute the risk of DLT within each third. We assign 20% of the overall risk of DLT during the first third, 30% during the middle third, and 50% of the risk during the last third of the 10-week assessment period.

There are 4 dose levels for this study (see [Table 4](#)), with the first group of patients starting at Dose Level 1. Dose Level -1 will be utilized if the toxicity profile for Dose Level 1 is shown to be unacceptable. The TITE-BOIN design will be used for dose escalation decisions. Whereas most Phase 1 dose escalation designs are based on occurrence of a DLT, the TITE-BOIN design uses a dose escalation algorithm that incorporates time to experiencing a DLT, thereby accounting for patients who have not completed their DLT assessment period (pending patients).

A TITE-BOIN design requires the level of DLT risk that one can tolerate. For the design below, this risk is set to 30%. In the design one also chooses a target interval of DLT risk; the TITE-BOIN design assigns dose levels based on the highest likelihood of DLT risk being within this range. That is, the dose escalation strategy seeks the dose level with the highest probability of being within this interval given the information already observed. Operationally, we will stop considering any dose (or higher doses) if the data lead to the conclusion that there is 95% probability that this dose is greater than the MTD.

[figure not shown]
We will use a cohort size of 3 patients for dose escalation decisions based on the TITE-BOIN design. The first cohort will receive 300 mg/m² (Dose Level 1) of LC weekly. The proposed target DLT risk is 30%, and the target DLT range is (23.6%, 35.9%). The dose escalation algorithm will drop doses at or above any dose for which the

observed data suggest there is 95% probability that this dose results in a DLT rate above 30%. Patient enrollment to the escalation phase will stop when 12 patients are assigned to the same dose or 24 patients have been enrolled, whichever happens first. Details of TITE-BOIN design are available at the website <https://trialdesign.org/one-page-shell.html#TITE-BOIN>.

8.4.9 Dose Escalation Algorithm

Figure 2 illustrates the dose escalation scheme based on TITE-BOIN design.

Figure 2. Dose Escalation Algorithm

$$* \text{ Predicted DLT rate} = \frac{\text{Predicted total number of patients who experienced DLT at the current dose}}{\text{Total number of evaluable patients treated at the current dose}}$$

DLT = dose-limiting toxicity; MTD = maximum tolerated dose

Similar to 3+3 design, in the TITE-BOIN design, when a new patient is ready to enroll in the dose escalation phase, the dose level to be assigned will depend on the outcome of patients who are assigned to the current dose level. For each dose level, the decision whether a new patient should be assigned to the current dose level (stay), the next higher dose level (escalation), or the next lower dose level (de-escalation) is provided in [Table](#)

10. The first column is the number of evaluable patients who have been assigned to the current dose level, the second column is the number of patients who experienced DLT at the current dose level, and the third column is the number of patients whose DLT data are pending at the current dose level. In the last column, “Yes & Eliminate” means the next patient will be dosed at the next lower dose level (de-escalation); the current and all higher dose levels will be eliminated from further dosing. Weighted standardized follow-up time (WSTFT) represents a weighted sum of the DLT intervals achieved in patients dosed at the current dose level. Online WSTFT computation is available from the website <https://trialdesign.org/one-page-shell.html#TITE-BOIN>.

Table 10. TITE-BOIN Design Dose Escalation and De-escalation Rules at Each Dose Level

# Evaluable patients	# DLTs observed	# Pending patients	Escalation	Stay	De-escalation
3	0	<=1	Yes	No	No
3	0	>=2	Suspend	Suspend	Suspend
3	1	0	No	Yes	No
3	1	1	No	WSTFT>0.88	WSTFT<=0.88
3	1	>=2	Suspend	Suspend	Suspend
3	2	<=1	No	No	Yes
3	3	0	No	No	Yes & Eliminate
6	0	<=3	Yes	No	No
6	0	>=4	Suspend	Suspend	Suspend
6	1	<=1	Yes	No	No
6	1	2	WSTFT>=0.6	WSTFT<0.6	No
6	1	3	WSTFT>=1.96	WSTFT<1.96	No
6	1	>=4	Suspend	Suspend	Suspend
6	2	0	No	Yes	No
6	2	1	No	WSTFT>0.73	WSTFT<=0.73
6	2	2	No	WSTFT>1.8	WSTFT<=1.8
6	2	3	No	WSTFT>2.87	WSTFT<=2.87

6	2	>=4	Suspend	Suspend	Suspend
6	3	<=3	No	No	Yes
6	>=4	<=2	No	No	Yes & Eliminate
9	0	<=4	Yes	No	No
9	0	>=5	Suspend	Suspend	Suspend
9	1	<=4	Yes	No	No
9	1	>=5	Suspend	Suspend	Suspend
9	2	0	Yes	No	No
9	2	1	WSTFT>=0.59	WSTFT<0.59	No
9	2	2	WSTFT>=1.65	WSTFT<1.65	No
9	2	3	WSTFT>=2.71	WSTFT<2.71	No
9	2	4	WSTFT>=3.77	WSTFT<3.77	No
9	2	>=5	Suspend	Suspend	Suspend
9	3	0	No	Yes	No
9	3	1	No	WSTFT>0.58	WSTFT<=0.58
9	3	2	No	WSTFT>1.65	WSTFT<=1.65
9	3	3	No	WSTFT>2.72	WSTFT<=2.72
9	3	4	No	WSTFT>3.79	WSTFT<=3.79
9	3	>=5	Suspend	Suspend	Suspend
9	4	<=5	No	No	Yes
9	>=5	<=4	No	No	Yes & Eliminate
12	0	<=6	Yes	No	No
12	0	>=7	Suspend	Suspend	Suspend
12	1	<=6	Yes	No	No
12	1	>=7	Suspend	Suspend	Suspend

12	2	<=3	Yes	No	No
12	2	4	WSTFT>=1.33	WSTFT<1.33	No
12	2	5	WSTFT>=2.72	WSTFT<2.72	No
12	2	6	WSTFT>=4.11	WSTFT<4.11	No
12	2	>=7	Suspend	Suspend	Suspend
12	3	<=6	No	Yes	No
12	3	>=7	Suspend	Suspend	Suspend
12	4	0	No	Yes	No
12	4	1	No	WSTFT>0.43	WSTFT<=0.43
12	4	2	No	WSTFT>1.5	WSTFT<=1.5
12	4	3	No	WSTFT>2.57	WSTFT<=2.57
12	4	4	No	WSTFT>3.65	WSTFT<=3.65
12	4	5	No	WSTFT>4.72	WSTFT<=4.72
12	4	6	No	WSTFT>5.79	WSTFT<=5.79
12	4	>=7	Suspend	Suspend	Suspend
12	5, 6	<=7	No	No	Yes
12	>=7	<=5	No	No	Yes & Eliminate

DLT = dose-limiting toxicity; TITE-BOIN = time-to-event Bayesian optimal interval; WSTFT = weighted standardized follow-up time

8.5 Feasibility Estimation

The feasibility is estimated by the proportion of patients who are evaluable for DLT assessment defined as defined as patients being able to complete 80% of the planned doses of LC, 80% of RT and 60% of TMZ within the first 10 weeks of treatment among all treated patients together with 95% confidence interval. Since this is the first time this treatment combination will be studied, this estimated proportion of evaluable patients will be used as reference for a future Phase 2 study to assess the feasibility of this treatment regime.

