3 OBJECTIVES AND ENDPOINTS

Table 3. Objectives and Endpoints

Objective	Endpoint
Primary	

 To determine the MTD/RP2D of LC in combination with RT and TMZ and adjuvant TMZ in newly diagnosed HGG To determine the safety and tolerability of LC infused IV over 3 hr 	
 Number of observed DLTs (as defined in Section 4.1.1)
Secondary	

 To estimate safety and tolerability of LC in combination with standard RT/TMZ and adjuvant TMZ To determine feasibility of weekly LC infusion as defined as patients being able to complete 80% of the planned doses of LC, 80% of RT and 60% of TMZ within the first 10 weeks of treatment To assess efficacy 	
 Safety assessments include SAEs, AEs, findings on physical examination, clinical laboratory findings, and ECGs Proportion of patients at each dose level who receive at least 80% of the planned infusions of LC 80% of RT and 60% of TMZ within the first 10 weeks of treatment OS and PFS at each dose level, PFS based on RANO criteria

AE = adverse event; DLT = dose-limiting toxicity; ECG = electrocardiography; HGG = high-grade glioma; IV = intravenously; LC = liposomal curcumin; MTD = maximum tolerated dose; OS = overall survival; PFS = progression-free survival; RP2D = recommended phase 2 dose; RANO = Response Assessment in Neuro-Oncology; RT = radiation therapy; SAE = serious adverse event; TMZ = temozolomide

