4.1.1 Dose-Limiting Toxicities

The DLT assessment period for this study is 10 weeks: 6 weeks of concurrent LC and CRT, and 4 weeks of single-agent LC.

Hematological Toxicities

Hematological toxicities will be considered dose limiting if any of the following occur and complete blood counts (CBCs) and differentials were obtained according to the mandated schedule (CBC, differential, and platelet count drawn twice a week until the ANC \geq 1500/ μ L and platelet count \geq 100,000/ μ L):

- ANC < 500/ μ L
- Platelet count < 25,000/ μ L
- Grade 4 anemia
- Grade 3 hemolysis
- Febrile neutropenia
- Any hematological toxicity that prevents administration of \geq 80% of the planned LC dose

Grade 3 or 4 lymphopenia will not be considered a DLT.

Central Nervous System Toxicities

Central nervous system (CNS) toxicities are:

- \geq Grade 2 CNS ischemia

- \geq Grade 2 neurological toxicities that interfere with activities of daily living and do not resolve spontaneously or with steroids, anticonvulsants, or electrolyte correction within 2 weeks
- Symptomatic CNS hemorrhage of any grade

Nonhematological, Non-CNS Toxicities

Grade 3 and 4 nonhematological, non-CNS toxicities will be considered DLTs, with the following exceptions:

- Grade 3 nausea, vomiting, or diarrhea despite sufficient prophylaxis with a duration < 3 days
- Alopecia
- Grade 3 fatigue
- Grade 3 hyperglycemia that is reversible and without clinical symptoms
- Grade 3 electrolyte disturbances that are asymptomatic and reversible within 3 days, and do not re-occur upon continuing or re-initiation at the same dose
- Grade 3 or 4 hypophosphatemia, unless considered clinically relevant
- Grade 3 or 4 elevations in alkaline phosphatase
- Grade 3 hypertension that resolved to \leq Grade 2 hypertension within 1 week either spontaneously or upon implementation of antihypertensive therapy
- A first episode of deep venous thrombosis (DVT) or pulmonary embolism

Hepatic DLTs are:

- ALT or AST > 8 *upper limit of normal (ULN), regardless of duration
- ALT or AST > 5 *ULN and ≤ 8 *ULN that fails to return to \leq Grade 1 within 2 weeks despite medical intervention
- Total bilirubin > 5 *ULN
- ALT or AST > 3 *ULN and concurrent total bilirubin > 2 *ULN

FOR PATIENTS ON CONCURRENT TREATMENT, ANY DLT (AS DEFINED ABOVE) CAUSING DELAY IN TREATMENT OF OVER 7 DAYS WITHOUT RECOVERY TO A \leq GRADE 1 OR BASELINE STATUS WOULD RESULT IN TAKING THE PATIENT OFF CONCURRENT TREATMENT.

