Once the MTD is determined, an additional 6 patients will be treated in an expansion cohort at this dose level or at a lower dose level determined to be the RP2D. For the expansion cohort, patients will continue to be monitored for occurrence of DLTs. If 2 of the first 5 patients or if ≥ 2 of 6 patients experience a DLT, the Principal Investigator will discuss with all study Investigators and with the Medical Monitor and/or SRC whether further addition of patients is needed to re-assess the MTD. Monitoring of all safety and toxicity data will be done by the Principal Investigator and the SRC on a real-time basis.

In the absence of treatment delays due to AEs, treatment for an individual patient may continue until the completion of standard therapy (until the end of Adjuvant Cycle 6) or until one of the following criteria applies:

- Disease progression

- Intercurrent illness that prevents further administration of treatment
- Unacceptable AEs
- Patient decides to withdraw from the study
- General or specific changes in the patient's condition render the patient unacceptable for further treatment in the judgment of the Investigator
- Clinical progression
- Patient noncompliance
- Pregnancy
- Termination of the study by the Sponsor
- The drug manufacturer can no longer provide the study agent

Toxicities requiring dosing delay or modifications will result in dose adjustments as outlined in [Section 5.10](#) (the minimum dose is 240 mg/m²).

Additional details of the study design and escalation decisions are in [Section 9](#).

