4.1.5 Evaluation of Toxicity and Response

- For dose escalation purposes, the DLT evaluation period is defined as the first 10 weeks of treatment (ie, 6 weeks of CRT plus LC followed by a 4-week post-CRT period).
 - Patients are available for DLT evaluation if they have either:
 - Received at least 80% of the planned doses of LC (8 of the planned 10 doses), at least 80% of the planned RT, and at least 60% of the planned TMZ
- OR

- Experienced a DLT in the first 10 weeks of treatment
- Dose finding will be performed using a TITE-BOIN schema as outlined in [Section 8.4.9](#). The window for DLT evaluation and decisions regarding dose advancement or de-escalation will be based on events occurring during the first 10 weeks of the study, though further data regarding safety and tolerability will be collected on every patient continuing infusions through the adjuvant TMZ treatment period.
- Standard contrast magnetic resonance imaging (MRI) will be used for assessment of progression, following the Response Assessment in Neuro-Oncology (RANO) criteria for PD. Patients will have a baseline MRI study followed by CRT, an MRI at the beginning of the adjuvant TMZ phase (4 weeks after completion of CRT) and another MRI every 2 cycles thereafter as per standard of care. More frequent imaging may be clinically necessary per the discretion of the treating physicians.
- MRI scans will be assessed locally by board-certified neuroradiologists who will independently assess tumor size and radiographic changes.
- For the first 2 years after the last dose of LC, patients will be followed for survival and progression every 2 months by telephone call, clinic visit, or medical records. After 2 years have elapsed, patients will be followed every 6 months for survival and progression by telephone call, clinic visit, or medical records.
- For the purposes of analyses, the duration of each arm will last through the 6 weeks of CRT, the 4-week post-CRT period, and the adjuvant cycles received by the patient.

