8.3 Populations for Analyses

For purposes of analysis, the following populations are defined:

Table 9. Populations for Analysis

Population	Description
Enrolled	All patients who sign the ICF
Evaluable (Escalation Phase)	All escalation patients who receive at least 80% of the planned doses of LC, 80% of planned RT, and 60% of planned TMZ in the first 10 weeks or experience a DLT prior to receiving 10 doses of LC
Efficacy Evaluable (Expansion Phase)	All expansion patients who receive at least 1 dose of LC and have baseline and at least one post-baseline tumor assessment.
Safety	All patients who receive at least 1 dose of LC. Patients will be analyzed according to the dose level they actually receive.

DLT = dose-limiting toxicity; ICF = Informed Consent Form; LC = liposomal curcumin; RT = radiation therapy; TMZ = temozolomide

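### Section 8.5 describes one feasibility estimate in two incompatible ways: the proportion evaluable for DLT, which takes in DLT patients by rule, and the proportion completing treatment

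*Protocol*

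**What the plan says.** Section 8.5 names the estimator: "The feasibility is estimated by the proportion of patients who are evaluable for DLT assessment". The same sentence then describes the group as "patients being able to complete 80% of the planned doses of LC, 80% of RT and 60% of TMZ within the first 10 weeks", taken among all treated patients with a 95% confidence interval. The section closes with the intended use: "this estimated proportion of evaluable patients will be used as reference for a future Phase 2 study".

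The feasibility endpoint in Table 3, repeated in Table 1, is completion only. It begins "Proportion of patients at each dose level who receive at least 80% of the planned infusions of LC" and adds the RT and TMZ cut-offs.

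Evaluability is defined elsewhere, and each definition has a second route:
- Section 4.1: a patient with a DLT is evaluable after a single LC dose.
- Section 4.1.5: the alternative to completion is "Experienced a DLT in the first 10 weeks of treatment".
- Table 9 (Section 8.3): the escalation-phase Evaluable population is completers "or experience a DLT prior to receiving 10 doses of LC".

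Section 4.1.1 also lists as a DLT "Any hematological toxicity that prevents administration of" at least 80% of the planned LC dose.

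**The concern.** The label and the definition in Section 8.5 select different patients. Someone stopped by a DLT after one infusion is evaluable under 4.1, 4.1.5 and Table 9, but has not completed. The clash is unavoidable for the hematological criterion in 4.1.1: toxicity that keeps LC below 80% of plan is itself a DLT, so that patient is evaluable and fails the completion test at once.

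Table 9 supplies a ready-made Evaluable population, and the last sentence of 8.5 again speaks of evaluable patients, so an analyst could reasonably take the numerator from that flag. The resulting figure would not fall when DLTs become more frequent, and would usually rise, which is the wrong direction for a tolerability measure. It is also the figure the protocol names as the reference for Phase 2.

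**Working it through.** **The plan's own count.** Six weekly LC doses during CRT plus four after it give 10; 0.80 × 10 = 8. This reproduces the 8 of 10 in Section 4.1.5. The protocol states no feasibility target.

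**Inputs**
- d, DLT risk: 30% target (Sections 4.1.2 and 8.4.8); 10% and 40% for comparison.
- DLT timing: 20%, 30% and 50% of the risk in successive thirds of the 10 weeks (Section 8.4.8). Risk is assumed uniform within each third.
- Eighth infusion: Day 50 in the schedule of activities, 7.0 weeks after Day 1.
- c0, completion rate among patients not stopped by a DLT: not given, so assumed at 70% to 100%.

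**Share of DLTs before the eighth infusion**

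F = 0.20 + 0.30 + 0.50 × (7.0 − 6.667)/3.333 = 0.55

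**Formulas**
- Evaluable reading: E = (1 − d)c0 + d
- Completion, LC stopping at the DLT: C1 = (1 − d)c0 + d(1 − F)c0
- Completion, no DLT patient completing: C2 = (1 − d)c0
- Overstatement: E − C1 = d[1 − (1 − F)c0], or E − C2 = d

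**At d = 30%, c0 = 100%**
- E = 0.70 + 0.30 = 100%
- C1 = 0.70 + 0.30 × 0.45 = 83.5%, a gap of 16.5 points
- C2 = 70%, a gap of 30 points

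With c0 between 90% and 70%, the first gap is about 18 to 21 points (0.30 × 0.595 to 0.30 × 0.685). The second stays at 30.

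**Direction, with c0 = 80%**

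| d | E | C1 | C2 |
|---|---|---|---|
| 10% | 82% | 75.6% | 72% |
| 30% | 86% | 66.8% | 56% |
| 40% | 88% | 62.4% | 48% |

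E rises with the DLT risk whenever c0 is below 100%; both completion figures fall.

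**At the escalation maximum of 24 patients** (d = 30%, c0 = 100%, nearest whole counts, exact 95% intervals)
- Evaluable: 24/24 = 100% (85.8% to 100%)
- Completion, LC stopping at the DLT: 20/24 = 83.3% (62.6% to 95.3%)
- Completion, no DLT patient completing: 17/24 = 70.8% (48.9% to 87.4%)

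**Population mismatch.** The Table 9 Evaluable set covers escalation patients only. Section 8.5 takes all treated patients as its base, which would include the up to 6 expansion patients. The flag therefore does not cover that denominator.

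**The case against.** The strongest reply is that Section 8.5 defines its own term. The completion cut-offs follow the label in the same sentence, contain no DLT route, keep every treated patient in the denominator and agree with Tables 1 and 3. On that text, a patient stopped by a DLT after one infusion is not feasible, and the overstatement is zero. This stands. A reader might infer that 8.5 settles that DLT patients score as feasible; it does not. It leaves two descriptions in conflict, and the closing sentence reverts to the evaluable one.

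Two further inferences are tempting and not supported:
- *That 8.5 wrongly pools dose levels.* Its mention of all treated patients sets a denominator. Table 3 asks for each dose level, and Section 8.4 already requires summaries by dose level and overall.
- *That counting infusions rather than mg/m² is an error.* The objective is feasibility of a weekly infusion, and a count is a coherent measure of that. Section 8.4.3 separately summarizes total dose and adjustments. The criticism depends on within-patient reduction, on which the protocol is inconsistent. Section 4.1.2 says "Toxicities requiring dosing delay or modifications will result in dose adjustments as outlined in" Section 5.10, with a 240 mg/m² minimum; 5.10 contains no patient-level steps; and 4.1 holds the dose constant within a cohort.

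The consequence is also limited. Section 8.1 makes all analyses descriptive, and 8.5 attaches no threshold or go/no-go rule to the figure.

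**Conclusion.** Section 8.5 is wrong as written, as an internal contradiction: one estimator has two descriptions that classify non-completing DLT patients differently. If the Table 9 flag were used, the overstatement would equal the share of treated patients who have a DLT and do not complete. At the 30% target that is 16.5 points if LC stops at the DLT and everyone else completes, and 30 points if no DLT patient completes. The 16.5 rests on the protocol's DLT timing, uniform risk within thirds and an assumed c0 of 100%. It is not a strict floor: DLT patients who continue LC and complete would shrink the gap. If the completion definition is followed, nothing is overstated. Since the endpoint is secondary and descriptive but is the named reference for Phase 2, severity is minor to moderate.

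**What to change.** In Section 8.5:
- Remove the evaluability label from the first sentence, and in the last sentence refer to the proportion of patients meeting the completion criteria.
- State that the denominator is every patient who received at least one LC dose, in escalation and expansion.
- State that DLT patients who miss any of the three cut-offs count as not feasible.
- Report by dose level and overall, as Table 3 and Section 8.4 already require.

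Keep the infusion count as the endpoint. Sections 4.1, 4.1.2 and 5.10 must be reconciled on whether LC is adjusted within a patient. If it is, show the total-dose summary from Section 8.4.3 beside the feasibility figure.

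The cost is a few sentences of protocol text. No new data are needed and the endpoint does not change. The reported figure would be lower only in comparison with one taken from the Table 9 flag.

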4.1.2 Dose Escalation

Following tumor resection, eligible patients who have signed the Informed Consent Form (ICF) will be assigned a dose of LC.

There will be a maximum of 4 dose levels assessed in this study. The first cohort of patients will start at Dose Level 1 (Table 4). If indicated based on the number of observed DLTs at Dose Level 1, patients may be enrolled in Dose Level -1.

Table 4. Liposomal Curcumin, Radiotherapy, and Temozolomide Dose Escalation Schedule

Dose Level	Dose	
	LC	TMZ
Level -1	240 mg/m ²	75 mg/m ² concurrent RT 150-200 mg/m ² Cycles 1-6 adjuvant
Level 1 (Starting Dose)	300 mg/m ²	
Level 2	350 mg/m ²	
Level 3	400 mg/m ²	

LC = liposomal curcumin; RT = radiotherapy; TMZ = temozolomide

The decision whether a new patient should be assigned to the current dose level or to a higher or lower dose level (escalation or de-escalation) is a function of the number of patients already treated at the current dose level, the number of patients who experienced a DLT at the current dose level, and the number of patients who have neither experienced a DLT nor completed their 10-week DLT evaluation period. The Safety Review Committee (SRC) will oversee dose level decisions throughout the dose escalation phase of the study.

All participating sites are expected to notify the Sponsor when a DLT has occurred.

The study will enroll and treat patients in cohorts of 3 in the dose escalation phase. The first cohort will receive 300 mg/m² (Dose Level 1) of LC weekly. The target DLT risk is 30%. During the assessment window, planned doses will be dropped if the data suggest a $\geq 95\%$ probability that the dose will produce a DLT risk $> 30\%$. Using the proposed time-to-event Bayesian optimal interval (TITE-BOIN) design, enrollment in the escalation phase will stop when 12 patients are assigned to the same dose level or when a total of 24 patients have been treated, whichever happens first.

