8.2 Sample Size Determination

The study will enroll up to 24 patients in the dose escalation phase. Once the MTD is established, accrual may continue in the dose expansion phase with the objective of studying 6 additional patients at the MTD dose determined in the escalation phase.

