8.4 Statistical Analyses

Summaries will be presented by dose level and over all dose levels. The summaries will present descriptive statistics (mean, standard deviation, median, minimum, and maximum) for continuous variables and frequencies and percentages for categorical variables.

Exact 95% confidence intervals may be generated for select endpoints. All data will be included in patient listings.

The statistical analysis plan (SAP) will be developed and finalized prior to database lock. The SAP will provide additional details on the statistical analyses, including procedures for accounting for missing data and outliers.

A high-level summary of the planned statistical analyses of the primary and secondary endpoints is presented below. If there are any differences between the analyses described in the protocol and the SAP, the SAP will prevail.

8.4.1 *Disposition and Demographics*

Summaries and descriptive statistics of demographic and baseline characteristics will be provided. Descriptive statistics for age, gender, race, ethnicity, height, weight, and body mass index will be generated.

Study and treatment completion status will be summarized, with reasons for premature discontinuation of treatment and of the study presented.

A summary of the number of patients in each study population will also be generated.

8.4.2 *Baseline Characteristics and Protocol Deviations*

Baseline characteristics and number of protocol deviations (any, minor and major) will be summarized overall and by dose group.

8.4.3 *Drug Exposure*

Drug exposure will be summarized based on the number of doses received for each study treatment (LC, CRT and RT) as well as the total dose received (separately for LC, CRT and RT), the number of cycles of CRT and the duration of treatment for LC, CRT and RT. Dose interruptions and adjustments will also be summarized.

8.4.4 *Karnofsky Performance Scale*

Scores on the KPS will be summarized at each assessment. Shift tables from baseline to maximum observed KPS score may also be generated.

8.4.5 *Concomitant Medications*

Concomitant medications will be summarized using the World Health Organization Drug Dictionary (WHODrug). Prior concomitant medications (medications used prior to study enrollment and stopped prior to the first study drug administration) will be summarized separately.

8.4.6 *Safety Analyses*

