8.6 Dose Expansion

An expansion cohort will be enrolled after the MTD has been determined in the escalation portion of the study. A maximum of 6 patients will be enrolled in the expansion cohort, dosed at the MTD. Expansion patients will continue to be monitored for safety to ensure that the DLT risk does not exceed 30%. Specifically, if more than 2 patients in the expansion cohort experience a DLT, an ad hoc SRC meeting may be convened to discuss the acceptability of the MTD.

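### Section 8.5 carries one feasibility proportion, pooled over all treated patients, into Phase 2, although the endpoint is defined at each dose level and the study seeks a single dose

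*Protocol*

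**What the plan says.** The secondary feasibility endpoint in Protocol Table 3 (Section 3) is the "Proportion of patients at each dose level who receive at least 80% of the planned infusions of LC", together with the radiotherapy and temozolomide criteria, in the first 10 weeks. Table 1 in the synopsis has the same by-dose definition.

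Section 8.5 is the only section that says how feasibility is estimated. It takes the proportion "among all treated patients together with 95% confidence interval", names no dose stratum, and adds that "this estimated proportion of evaluable patients will be used as reference for a future Phase 2 study".

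Other relevant statements:

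- Section 8.4, as a general rule: "Summaries will be presented by dose level and over all dose levels".
- Section 4.1.2: "There will be a maximum of 4 dose levels assessed in this study". Table 4 lists them as 240, 300, 350 and 400 mg/m².
- Section 8.2: "The study will enroll up to 24 patients in the dose escalation phase". Under Section 4.1.2, "enrollment in the escalation phase will stop when 12 patients are assigned to the same dose level" if that happens before 24 have been treated.
- Section 8.6: "A maximum of 6 patients will be enrolled in the expansion cohort, dosed at the MTD".
- Section 7.1.3.2: one RP2D is chosen after review of the safety data by dose level.

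**The concern.** The endpoint tables ask how many patients can complete treatment at a given dose. Section 8.5 answers a different question: how many can complete it on average over whatever mix of doses the escalation produced. It is this second figure that receives the confidence interval and goes forward to Phase 2.

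The protocol itself ties completion to dose. In Section 4.1.1, a hematological toxicity that keeps a patient below 80% of planned LC is a DLT, and it is also a failure of the LC feasibility criterion. The same section takes patients with a prolonged unresolved DLT off concurrent treatment, and Section 6.1.2 rules out LC rechallenge after a DLT that required stopping it. Every Table 11 scenario with stated DLT rates has those rates rising with dose.

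A Phase 2 trial at one dose needs the completion rate at that dose. A pooled rate depends partly on how many patients the escalation placed above and below it, so two trials with the same true rate at the MTD could hand different references to Phase 2.

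**Working it through.** The protocol states no feasibility rate, target or precision, so there is no figure to reproduce. The total agrees with the synopsis: 24 escalation + 6 expansion = 30 patients.

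**Step 1. Share of the denominator at another dose.** Inputs are the mean number of patients and the percentage treated at each dose in Table 11, plus 6 expansion patients. *Assumption:* all 6 are at the dose whose true DLT rate is 0.30.

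- Scenario 1: 0.495 × 18.2 + 6 = 15.0 of 24.2 at the MTD; 38% at another dose.
- Scenario 2: 0.498 × 20.7 + 6 = 16.3 of 26.7; 39% at another dose.
- Scenario 3: 0.418 × 21.6 + 6 = 15.0 of 27.6; 46% at another dose.

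Scenario 4 is not used because its rows as read repeat Scenario 3 and show no true DLT rates. Scenario 5 is not used because no dose has a DLT rate of 0.30.

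The sample-size rules alone give a bound. If escalation runs to 24 patients with at most 12 at one dose, and 6 more are added there, at most 18 of 30 share a dose and at least 12/30 = 40% had another. If instead the first 12 patients all stay at the starting dose and the expansion is at that dose, nobody had another dose and the two figures coincide.

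**Step 2. Pooled figure against the figure at the MTD.** *Assumption:* feasibility at a dose = 1 − true DLT rate. This is illustrative. Some DLTs will not prevent completion, and some patients will fail to complete without a DLT.

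Pooled = Σ(patients at dose × feasibility at dose) / Σ(patients at dose). At the MTD the assumed feasibility is 1 − 0.30 = 70.0%.

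- Scenario 1: (15.01 × 0.70 + 7.46 × 0.53 + 1.53 × 0.45 + 0.20 × 0.36) / 24.20 = 15.22 / 24.20 = 62.9%; difference −7.1 points.
- Scenario 2: (4.82 × 0.89 + 16.31 × 0.70 + 4.74 × 0.55 + 0.85 × 0.33) / 26.72 = 18.60 / 26.72 = 69.6%; difference −0.4 points.
- Scenario 3: (0.86 × 0.98 + 7.97 × 0.87 + 15.03 × 0.70 + 3.76 × 0.53) / 27.62 = 20.29 / 27.62 = 73.5%; difference +3.5 points.

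The last two denominators slightly exceed 26.7 and 27.6 because the printed percentages sum to 100.1. If every rate is multiplied by 0.9, to allow for non-completion unrelated to DLTs, the differences become −6.4, −0.4 and +3.1 points.

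**Step 3. Price in precision.** Exact (Clopper-Pearson) 95% intervals for assumed counts:

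- 12/15 = 80% at one dose: 52% to 96%.
- 14/18 = 78% at one dose, with 18 = 12 + 6: 52% to 94%.
- 24/30 = 80% pooled: 61% to 92%.

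**The case against.** The strongest reply is that the phrase about all treated patients only fixes the denominator as treated rather than evaluable patients, and that the by-dose definition in Tables 1 and 3 still governs. Section 8.4 uses explicit words when it means pooling over doses. This reading is possible but strained: 8.5 names no stratum, speaks of one estimated proportion with one interval, and gives that single figure a use.

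Second, by-dose figures will be tabulated anyway under Section 8.4, which also allows exact intervals for selected endpoints and lets the SAP prevail. This stands, and it narrows the point. A reader might infer that dose-level feasibility would be lost; the documents do not support that. What the general rule leaves unchanged is which figure 8.5 names as the Phase 2 reference.

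Third, pooling has some logic. The objective concerns weekly LC with standard therapy, and the planned radiotherapy, temozolomide and infusion schedule are common to all dose levels. That justifies showing a pooled figure, which is also more precise. It does not make it the right reference for one dose, given the links between DLTs and completion.

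Fourth, the shares in Step 1 place the whole expansion cohort at the true MTD. Table 11 shows that dose selected in only 61.6%, 62.0% and 58.9% of simulations in Scenarios 1 to 3, and Section 4.1.2 allows expansion at a lower RP2D. The shares are therefore conditional on that assumption and do not follow from Table 11 alone.

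**Conclusion.** The point holds in a limited form. Section 8.5 conflicts with Tables 1 and 3 on the stratum of the feasibility estimate, and it carries the pooled figure forward although one dose is sought.

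On the stated assumptions, about 38% to 46% of the pooled denominator had a dose other than the MTD, and the pooled figure is off by roughly −7 to +3.5 points, close to zero in Scenario 2.

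A reader might infer that pooling always makes the regimen look less feasible, because patients treated above the MTD drag the figure down. Assuming 80% feasibility at or below the MTD and 50% above it does give pooled values of 69%, 74% and 76% in Scenarios 1 to 3. But that step assumption lets the error run in one direction only, and the documents give no rates to support it. When feasibility falls steadily with the DLT rate, better completion at lower doses offsets the loss above the MTD and in Scenario 3 outweighs it. The direction cannot be known in advance.

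Severity is modest. Feasibility is a secondary endpoint, Section 8.1 makes all analyses descriptive, and 8.5 attaches no threshold or go/no-go rule to the figure.

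**What to change.** Reword Section 8.5 to match Tables 1 and 3. Estimate the proportion, with an exact 95% CI, among treated patients at each dose level. Name the estimate at the MTD/RP2D, from escalation and expansion patients treated at that dose, as the Phase 2 reference. Keep the proportion over all dose levels as a descriptive summary.

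This takes about one sentence and needs no extra patients, visits or data. The cost is precision: with 80% completing, the interval widens from 61–92% (24/30) to 52–96% (12/15). That width shows how much the study can say about the dose taken forward; the pooled interval is narrower only because it includes patients at other doses.
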